19.0 Analytical Plan

All statistical processing will be performed using SAS[®] version 9.3 or later, unless otherwise stated.

Descriptive statistics (i.e., number of subjects, mean, standard deviation, median, minimum, maximum) will be presented for all continuous variables; number and percentage of subjects will be presented for categorical variables. For parameters measured over time, observed data and changes from baseline will be described for each time point.

When feasible, based on adequate sample size sub-group analyses including by gender and by underlying condition will be conducted.

A Statistical Analysis Plan (SAP) describing all statistical analyses in detail will be provided as a separate document.

19.1 Sample Size Determination

This is an exploratory study with safety as a primary objective. As a result, no formal sample size calculations are defined and the data from this study will provide safety data for SCY-078 in patients along with a preliminary view of efficacy data, which can be used to design future studies. Given that this is early Phase 2 trial, it would be difficult to try to estimate a sample size that would be required to achieve some evidence of statistical superiority of the efficacy endpoints being evaluated. The sample size needed to achieve statistical superiority on all-cause mortality is much larger than is feasible for this early stage study. In addition there is insufficient information on effect size for the other endpoints such as global response and kinetics of galactomannan as a marker of efficacy. The main goal of this study is to obtain preliminary estimates of the effect size expected for all of the efficacy endpoints.

19.2 Analysis Populations

The study populations used for the analyses are as follows:

Intent-to-Treat (ITT)/Safety Population: The ITT Population will include all randomized subjects who receive at least one dose of randomized study medication. The Safety Population will be the same as the ITT population.

Modified Intent-to-Treat (mITT): The mITT population will be a subset of the ITT population that will include subjects who have a probable or proven IPA at baseline, per DRC, with at least one positive serum GMI at baseline.

Per-Protocol (PP) Population: The PP Population will be a subset of the ITT population and will include subjects who have a probable or proven IPA at baseline, per DRC, with at least one positive serum GMI at baseline, have completed at least 14 days of randomized study treatment and have at least one efficacy assessment post Baseline (Treatment Day 1) and no major protocol deviations.

PK Population: The PK Population will include all enrolled subjects who provide at least one PK sample.

19.3 Subject Disposition, Discontinuation, and Baseline Data

Subject disposition in terms of the number and percentage of subjects enrolled by site will be tabulated. The number of subjects enrolled, number completing the study and reasons for discontinuation will be summarized. Subject demographics and baseline characteristics such as age, race, ethnicity, sex, weight, height, body mass index, country and other relevant parameters will be tabulated.

Baseline is defined as the last non-missing assessment prior to the date (and time if appropriate) of the first dose of study drug. Change from baseline is defined as: post-baseline value – baseline value.

19.4 Handling of Missing Data, Dose Adjustments, and Early Withdrawals

For the efficacy analyses, subjects who do not have an EoT assessment will be assigned an indeterminate outcome, so will be classed as treatment failures for the corresponding efficacy analyses. For subjects who withdraw from the study early, every effort will be made to collect EoT visit information at the point of withdrawal.

19.5 Prior and Concomitant Medications

Prior and concomitant medications will be coded using the World Health Organization Drug Dictionary terminology. The number and percentage of subjects taking each medication before and after the first dose of study drug will be tabulated. Medications taken and stopped prior to the first dose of study drug will be considered prior medications. Medications started on or before the FU visit date with missing stop dates or stop dates after the first dose of study drug will be considered concomitant medications.

19.6 Safety

19.6.1 Safety Assessments

Subjects will be evaluated for safety and tolerability throughout the study, including parameters such as physical exam including visual function assessment, vital signs, 12-lead ECGs, safety laboratory tests (hematology, blood chemistry and urinalysis), concomitant medications, AEs and treatment discontinuations. Electrolyte disturbances such as hypokalaemia, hypomagnesaemia and hypocalcaemia should be monitored and corrected, if necessary, prior to initiation and during voriconazole therapy.

Safety procedures are described in **Section 15.0** and safety assessments are described in **Section 17.0**.

19.6.2 Safety Analyses

All safety analyses will be conducted using the ITT/safety population; all safety variables will be listed.

The incidence and severity of TEAEs and SAEs and their relationship to treatment will be summarized. AEs will be coded using the Medical Dictionary for Regulatory Activities (MedDRA) Version 19.1 or higher and presented by system organ class and preferred term.

Early discontinuation of study drug treatment will be presented and will include the reasons for and timing of such discontinuations.

Prior and concomitant medications will be summarized; medications will be classified based on the World Health Organization's Drug Dictionary terminology.

Abnormal physical examinations will be listed. Laboratory evaluations will be summarized as observed values and changes from Baseline; shifts with respect to the laboratory reference range will be summarized. Events of clinical interest will be summarized.

Vital signs and ECG evaluations will be summarized as observed values and changes from Baseline.

19.7 Efficacy

19.7.1 Efficacy Assessments

Efficacy will be assessed primarily in terms of Global Response, ACM and GMI decrease (GMI decrease will only be assessed for subjects with a Serum GMI above 0 at Baseline). The DRC evaluation of Global Response is considered the key efficacy evaluation, considering the expert and independent nature of the DRC assessment. In addition to Global Response, clinical, mycological and radiological outcomes will also be assessed. Exploratory efficacy assessments include, among others, recurrence, performance indicators and other serological biomarkers (β -D-glucan and *Aspergillus* PCR).

19.7.1.1 Treatment Outcome

Global Response will be assessed based on the following definitions:

- Global Response
 - Complete Response: Survival and resolution of all attributable symptoms and signs of disease; plus, successful radiological outcome; plus, documented mycological eradication of infected sites that are accessible to repeated sampling or presumed eradication of sites that are not accessible to repeated sampling.
 - Partial Response: Survival and improvement of attributable symptoms and signs of disease; plus at least 25% reduction in diameter of radiological lesion(s); plus, documented mycological eradication of infected sites that are accessible to repeated sampling or presumed eradication of sites that are not accessible to repeated sampling. In cases of radiological stabilization (defined as 0%-25% reduction in the diameter of the lesion), resolution of attributable symptoms and signs of fungal disease can be equated with a partial response. In cases of radiological stabilization, biopsy of an infected site (e.g., lung biopsy) showing no evidence of hyphae and negative culture results can be equated with a partial response.
 - Stable response: Survival and no improvement in any attributable symptoms and signs of disease; plus, radiological stabilization (defined as a 0%-25% reduction in the diameter of the lesion); or persistent isolation of mold or histological presence of invasive hyphae in infected sites.
 - Progression of disease: Worsening clinical symptoms and signs of disease; plus, new sites of disease or radiological worsening of preexisting lesions; or persistent isolation of mold species from infected sites.
 - Death: Death during the prespecified period of evaluation regardless of attribution.

Clinical, mycological and radiological outcome will be assessed based on the following definitions:

- Clinical response
 - Success:
 - Resolution of all attributable clinical symptoms and physical findings
 - Partial resolution of attributable clinical symptoms and physical findings
 - Failure:

- No resolution of any attributable clinical symptoms and physical findings and/or worsening
- Not applicable:
 - No attributable signs and symptoms present at Baseline and no symptoms attributable to invasive fungal disease developed post Baseline
- Mycological response
 - Success:
 - Eradication
 - Presumed eradication
 - Failure:

- Persistence
- Presumed persistence
- Not applicable:
- No mycological evidence available at Baseline
- Radiological response
 - Day 42:
 - Success (improvement of at least 25% from Baseline)
 - Failure
 - No post Baseline radiology available for patient with baseline evidence of radiological disease
 - Radiology not applicable at Baseline
 - Day 84:
 - Success (improvement of at least 50% from Baseline)
 - Failure
 - No post Baseline radiology available for patient with baseline evidence of radiological disease
 - Radiology not applicable at Baseline
 - EoT:
 - Success (improvement of at least 25% from Baseline if EoT occurs prior to Day 42; if EoT occurs after Day 42, at least 50% improvement from Baseline)
 - Failure
 - No post Baseline radiology available for patient with baseline evidence of radiological disease
 - Radiology not applicable at Baseline

19.7.1.2 All-Cause Mortality

All-cause mortality will be defined as death during the prespecified period of evaluation, regardless of attribution. Survival will be determined via an in-person visit or a phone contact, and will document subject status (alive or deceased) as well as date of death. If subject is deceased, the investigator's assessed relationship to the fungal infection will also be recorded. If autopsy is conducted, key findings should be collected in the eCRF.

19.7.1.3 GMI Decrease

GMI decrease will be assessed in terms of absolute and percentage reduction relative to Baseline, and in terms of time to achieve the GMI absolute and percentage reductions. GMI decrease will be assessed in subjects with Baseline serum GMI above 0, only.

19.7.1.4 Recurrence

Recurrence is defined as a diagnosis of probable or proven IPA based on EORTC after EoT in patients who have previously achieved complete response. Re-emergence of the *Aspergillus* infection is required to be with the same species (if *Aspergillus* isolates are available for both the baseline and the recurrent episode) and involving the same site that was initially identified at Screening. The DRC will be responsible for determining recurrence.

19.7.2 Efficacy Analyses

The secondary efficacy endpoint, the percentage of subjects with successful Global Response (Complete Response or Partial Response) at EoT, Day 42 and Day 84 as determined by the DRC and the Principal Investigator will be presented by treatment group along with an estimate of the difference between treatment groups. The response rate will be calculated for each treatment group as the number of successes divided by the total number of patients (success + failure + indeterminate). The difference in response rates between treatments will be presented along with a 95% confidence interval (CI), calculated using the method of Miettinen and Nurminen. The secondary analysis of ACM at Day 42 and Day 84 will be presented by treatment group along with an estimate of the difference between treatment groups. In addition, a Kaplan Meier plot will be produced to summarize overall survival over time.

The remaining secondary and exploratory endpoints will be summarized by treatment group.

Provided sufficient data are available to allow meaningful presentation, results of the key efficacy parameters will also be presented by baseline *Aspergillus* species; by baseline minimum inhibitory concentration (MIC) and minimal effective concentration (MEC) for voriconazole and SCY-078, respectively; and by baseline neutropenia and persistent neutropenia at Week 2.

Considering the exploratory nature of this study, further analysis may be defined in the statistical analysis plan, as deemed appropriate. For example, if the data are heterogeneous within this randomized study, attempts may be made to match patients across the treatment groups on key disease criteria, if sufficient data are available, to better understand the comparability of the randomized groups.

19.8 Pharmacokinetics

19.8.1 Pharmacokinetic Assessments

PK testing for the determination of SCY-078 will be conducted for all subjects. For the first 20 randomized subjects, blood samples for SCY-078 PK testing will be collected predose on Treatment Days 1, 3, 7 and 14, approximately within 1 hour before dosing, and on Treatment Days 1, 7 and 14 at 2-4 hours and at 6-8 hours after dosing.

Voriconazole level determination will also be performed for all study subjects predose on Treatment Days 1, 3, 7 and 14, approximately within 1 hour before dosing, and on

Treatment Days 1, 7 and 14 at 2-4 hours and at 6-8 hours after dosing.

The PK data from the first 20 subjects will be assessed in an interim PK analysis that will keep the study team blinded.

For subsequent randomized subjects, blood PK samples will be collected predose on Treatment Days 1, 3, 7 and 14, approximately within 1 hour before dosing, and on Treatment Days 1, 7 and 14 at 4-8 hours after dosing for SCY-078 and voriconazole central lab PK testing.

Results for plasma concentrations of SCY-078 and voriconazole analyzed by the central laboratory will not be available in real time for any subject.

19.8.2 Pharmacokinetic Analyses

The sparse samples collected in this study will be analyzed using Population PK (Pop PK) analysis methods to estimate PK parameters (C_{max} , AUC, clearance/fraction absorbed [CL/F]) as applicable.

Key collection and analysis timepoints include Day 1, Day 7 (i.e., steady state) and Day 14. After the first 20 subjects have been treated for at least 7 days, an interim PK evaluation will be conducted to ensure there are no clinically relevant effects of the co-administration of SCY-078 and voriconazole on the PK exposure (predicted AUC and C_{max} based on updated population PK model) of both drugs. The data from this analysis will inform, and if necessary adjust, the doses of the study drug for subjects subsequently randomized. The overall goal, considering that IPA is a life-threatening condition, is to ensure that >80% of subjects achieve an exposure that is at least equal to that reported as efficacious in the mice models of invasive aspergillosis (15.6 μ g•mL/hr). The results from the PK analyses will be presented in a separate report.

The interim analysis will be focused on PK parameters only. Unblinded information will

be provided to the independent pharmacokinetics team doing the analysis and the remaining of the study team will remain blinded. The statistical team responsible for randomization will confirm if at least 10 subjects have been randomized to SCY-078 and voriconazole at the time of the planned interim analysis. If less than 10 subjects have been randomized to SCY-078 and voriconazole at that point, the interim analysis will be postponed until 24 subjects are randomized.

20.0 Ethics and Protection of Human Patients

20.1 Ethical Conduct of the Study

The study will be conducted in accordance with the protocol, the ethical principles established by the Declaration of Helsinki (as amended in Fortaleza, Brazil, October 2013), the International Conference on Harmonisation (ICH) Good Clinical Practice (GCP) Guidelines, the US Code of Federal Regulations (CFR) sections that address clinical research studies, applicable European Union regulations and/or other national and local ethical and legal requirements, as applicable.

20.2 Institutional Review Board/Ethics Committee Review

The PI must provide the IRB/EC with all appropriate materials, including a copy of the subject ICF. The study will not be initiated until the PI obtains written approval of the protocol and the subject ICF from the appropriate IRB/EC, and copies of these documents are received by the Sponsor. Appropriate reports on the progress of this study will be made by the PI to the IRB/EC, medical monitor, and Sponsor in accordance with applicable government regulations and in agreement with policy established by the Sponsor.

20.3 Informed Consent

The ICH issued guidelines to provide protection for human subjects in clinical investigations. The ICH Tripartite Guideline for Good Clinical Practice establishes the general requirements for informed consent. Each subject will be provided with oral and written information in a language they can understand that describes the nature and duration of the study. Before undergoing screening, each subject must consent in writing to study participation. The patient (or the subject's legal representative) will sign and personally date the subject ICF. The person rendering consent will also sign and personally date the subject ICF as the person who obtained the consent of the subject. For subjects who were unable to provide consent due to incapacity and their legally authorized representative (LAR) provided consent on their behalf, and if during the course of the study, the subject regains the ability to make decisions he/she will be informed of the decisions made by the LAR during the time of their incapacity and any

effects that may have occurred as a result. The subject will then be asked to provide consent and decide whether to continue in the study. Alternatively, the site may choose not to include patients in the study, who are not able to provide consent on their own. The original signed subject ICF will be retained with the study center's records. Each subject will receive a copy of his/her signed subject ICF. In addition, the PI, or his or her designee, must document in the case history that informed consent was obtained before study participation.

20.4 Future Use of Samples

Mold isolates including *Aspergillus* spp. (see Section 15.14) collected in this study may be maintained in repositories for potential future use. Future research of isolates may include *in vitro* susceptibility testing of new or existing antifungals or analysis of mechanisms of resistance.

20.5 Subject Privacy and Subject Confidentiality

All laboratory specimens, evaluation forms, reports, and other records that leave the site will be identified only by a coded number to maintain subject privacy and confidentiality. All records will be kept in a locked file cabinet. All computer entry and networking programs will be performed with coded numbers only. Clinical information will not be released without written permission of the subject, except as necessary for monitoring by the medical monitor, IRB/EC, the Food and Drug Administration (FDA), the Sponsor or where required by law. All local privacy laws must be followed.

20.6 Study Termination

The PI, the Sponsor, the FDA, and the IRB/EC each reserve the right to terminate the study, due to unjustifiable risk, relevant toxicity, and/or unknown and new adverse event findings, in the interest of subjects' safety and welfare. The Sponsor reserves the right to terminate the study at any time for administrative or any reasons.

20.7 Financial Disclosure

The financial interests of all investigators from all participating clinical centers must be collected prior to study initiation and 1 year following the completion of the clinical trial.

22.0 Appendices

22.1 Appendix A: Prohibited Medications and Medications to be Administered with Caution

Below are a few examples relevant for hematological patients. Details and flexible medical monitor guidance will be available, with consideration to local label, local standard practice and best interest of the patient.

22.1.1 Prohibited Medications

In addition to the prohibited medications listed below, the Voriconazole label should be consulted and followed for additional warnings and precautions related to concomitant medications.

Investigational Drugs

No other investigational drugs are allowed during the study from at least 28 days or 5.5 half-lives of the investigational product (whichever is longer) before signing the informed consent through the 6-Week Follow-up visit.

Antifungals

- No antifungal treatment other than the study drug is allowed during the study.
- Prior mold-active antifungal agents for the treatment of the IPA episode are not allowed for more than 4 days (96 hours) in the 7 days preceding enrollment (Baseline/Treatment Day 1), except for those subjects who have received more than 4 days but less than 7 days of prior mold-active antifungal therapy for the treatment of the IPA episode in the 7 days preceding enrollment into the study and are approved for randomization by the medical monitor.
- Prophylaxis with a mold-active azole antifungal (i.e., voriconazole, posaconazole, isavuconazole or itraconazole) is not allowed in the 14 days preceding enrollment into the study (Baseline/Treatment Day 1).

Other Prohibited Medications

In addition, the medications listed below are also prohibited.

Strong CYP3A4/5 inhibitors and CYP3A4/5 inducers

СҮР	Strong Inhibitors ^a	Inducers ^a
-----	--------------------------------	-----------------------

			• avasimibe
	• boceprevir	• nefazodone	 carbamazepine
	• clarithromycin	• nelfinavir	• phenytoin
3A4/5	• conivaptan	• ritonavir	• rifampin
	• indinavir	• saquinavir	• St. John's wort
	lopinavir	• telaprevir	
	• mibefradil	• telithromycin	

a: The CYP3A4/5 inhibitors and CYP3A4/5 inducers listed in this table are not permitted during the 14 days prior to Baseline/Treatment Day 1 and during study treatment.

P-glycoprotein (P-gp) substrates

P-gp Drug Substrates ^a
digoxin, colchicine, vinblastine and talinolol

a. The P-gp substrates listed in this table are not permitted during the 48 hours prior to Baseline/Treatment Day 1 and during study treatment.

22.1.2 Medications to be administered with Caution and Monitored as Appropriate

CYP3A4 substrates

СҮР	Substrates		
3A4	In vitro, SCY-078 was an inhibitor of CYP3A mediated metabolism of midazolam, but		
	was only a weak inhibitor of metabolism of testosterone. The clinical significance of		
	this inhibition is unknown; caution should be exercised when administering SCY-078		
	with drugs known to be CYP3A sensitive substrates with narrow therapeutic index,		
	such as midazolam and cyclosporine.		
	Subjects receiving sirolimus, tacrolimus or warfarin, cyclosporine or amiodarone are		
	permitted for enrollment in the study and these medications may be administered		
	concomitantly with SCY-078 with close monitoring. Dosing adjustments and		
	subsequent monitoring of sirolimus and warfarin should be undertaken in accordance		
	with product prescribing information for the respective agents.		

OATP1B3 substrates

OATP	Substrate		
1B3	In vitro, SCY-078 is an inhibitor of the OATP1B3 liver uptake transporter. The		
	clinical significance of this inhibition is unknown; however, there is a potential risk		
	for increased exposure of the concomitant medications (arising from lowered hepatic		
	clearance) when administering SCY-078 with drugs known to be OATP1B3 selective		
	substrates. Therefore, caution should be exercised when administering SCY-078 with		
	drugs known to be OATP1B3 selective substrates such as telmisartan, including		
	monitoring the subject for signs of overexposure associated with the concomitant		
	medications as described in the product prescribing information.		

Sources:

- FDA Draft Guidance for Industry. Drug Interaction Studies Study Design, Data Analysis, and Implications for Dosing and Labeling. 2012.
- Drug interactions in infectious disease by Stephen C. Piscitelli, Keith Rodvold (2007)
- UCSF-FDA Transportal

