14.3 Medications to be Administered with Caution and Monitored as Appropriate

The following medications must be administered with caution and must be monitored as appropriate:

- Select CYP3A4 substrates, including but not limited to sirolimus, tacrolimus, warfarin, cyclosporine and amiodarone
- Organic anion-transporting polypeptide 1B3 (OATP1B3) substrates

A detailed list of medications to be administered with caution is provided in Section 22.1 (Appendix A).

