14.4 Voriconazole Drug Interactions

The systemic exposure to voriconazole is expected to be reduced by the concomitant administration of the following agents and their use is **contraindicated**:

- *Rifampin* (potent CYP450 inducer)
- *Rifabutin* (potent CYP450 inducer)
- *Ritonavir* (potent CYP450 inducer)
- St. John's Wort (CYP450 inducer; P-gp inducer)
- Carbamazepine and long-acting barbiturates (potent CYP450 inducers)

The systemic exposure of the following drugs is expected to be significantly increased by coadministration of voriconazole and their use is **contraindicated**:

- Sirolimus (CYP3A4 substrate)
- *Terfenadine, astemizole, cisapride, pimozide and quinidine* (CYP3A4 substrates)
- Ergot alkaloids

Coadministration of voriconazole with the following agents could result in significant drug

interactions that may require dosage adjustment, frequent monitoring of drug levels and/or frequent monitoring of drug-related adverse events/toxicity:

- Alfentanil (CYP3A4 substrate)
- Fentanyl (CYP3A4 substrate)
- Oxycodone (CYP3A4 substrate)
- Cyclosporine (CYP3A4 substrate)
- *Methadone* (CYP3A4, CYP2C19, CYP2C9 substrate)
- *Tacrolimus* (CYP3A4 substrate)
- Warfarin (CYP2C9 substrate)
- Oral Coumarin Anticoagulants (CYP2C9, CYP3A4 substrates)
- Statins (CYP3A4 substrates)
- Benzodiazepines (CYP3A4 substrates)
- Calcium Channel Blockers (CYP3A4 substrates)
- Sulfonylureas (CYP2C9 substrates)
- Vinca Alkaloids (CYP3A4 substrates)
- Non-Steroidal Anti-Inflammatory Drugs (NSAIDs; CYP2C9 substrates)
- *Efavirenz,* a non-nucleoside reverse transcriptase inhibitor (CYP450 inducer; CYP3A4 inhibitor and substrate)
- *Phenytoin* (CYP2C9 substrate and potent CYP450 inducer)
- *Omeprazole* (CYP2C19 inhibitor; CYP2C19 and CYP3A4 substrate)
- Oral Contraceptives (CYP3A4 substrate; CYP2C19 inhibitor)
- Other HIV Protease Inhibitors (CYP3A4 substrates and inhibitors)
- Other Non-Nucleoside Reverse Transcriptase Inhibitors (NNRTIs) (CYP3A4 substrates, inhibitors or CYP450 inducers)

Additional information regarding medications that are contraindicated or require specific precautions when coadministered with voriconazole can be found in Section 22.2 (Appendix B: Voriconazole Label).

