s. Samples for SCY-078 PK will be collected from all subjects. For the first 20 randomized subjects, blood PK samples will be collected predose on Treatment Days 1, 3, 7 and 14, approximately within 1 hour before dosing, and at 2-4 hours and 6-8 hours after dosing on Treatment Days 1, 7 and 14. The PK data from the first 20 subjects will be assessed in an interim PK analysis. For subjects subsequently randomized, blood PK samples will be collected predose on Treatment Days 1, 3, 7 and 14, approximately within 1 hour before dosing, and at 4-8 hours after dosing on Treatment Days 1, 7 and 14. The time of dosing and sample collection must be recorded in the eCRF and on the subject's medical record.

t. All randomized subjects will receive either SCY-078 + voriconazole or SCY-078 placebo + voriconazole.

u. For non-hospitalized patients only.

PROCEDURE Visit	Visit/contact Survival Day 42	Visit/contact Survival Day 84
Days (allowable window)	± 2	± 4
Assessment of treatment outcome	Х	x
Subject Status (alive/ deceased)	X	x
Karnofsky Score	X	x

Table 5Schedule of Treatment Visits and Procedures forDays 42 and 84(Study SCY-078-206)

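### The protocol lets sirolimus users enrol and stay on the drug (22.1.2) but lists sirolimus as contraindicated with voriconazole (14.4), which every randomized subject is assigned

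*Protocol*

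**What the plan says.** Protocol Section 22.1.2, on CYP3A4 substrates, gives a study-level permission. Its opening names five drugs, sirolimus first: "Subjects receiving sirolimus, tacrolimus or warfarin, cyclosporine or amiodarone are". What it then allows covers both entry to the trial and use during it: "permitted for enrollment in the study and these medications may be administered". The condition is that the subject is closely monitored while also taking SCY-078. The next sentence of 22.1.2 covers dose changes and later checks for sirolimus and warfarin, and refers sites to each drug's own label. Section 14.3 is the main-text counterpart. It lists as drugs to be used with caution "Select CYP3A4 substrates, including but not limited to sirolimus, tacrolimus, warfarin, cyclosporine and amiodarone".

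Section 14.4 deals with voriconazole. One of its lists covers drugs whose exposure is "expected to be significantly increased by coadministration of voriconazole and their use is" contraindicated, and sirolimus is the first entry. A separate list in 14.4 holds drugs that need dose adjustment or monitoring; tacrolimus, cyclosporine and warfarin are there.

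Footnote t to the schedule in Section 16.0 confirms that voriconazole is common to both arms: "All randomized subjects will receive either SCY-078 + voriconazole or SCY-078 placebo + voriconazole". Section 13.1.1 says the same.

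**The concern.** A drug cannot be both permitted under monitoring and contraindicated in the same subject. Section 22.1.2 is reasoned from SCY-078's own effect on CYP3A, but no subject in this trial is assigned SCY-078 or its placebo without voriconazole. A site that acts on the permission therefore gives sirolimus with voriconazole, for up to the 13-week treatment maximum.

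Such patients are foreseeable. The permission sentence itself anticipates sirolimus users, inclusion criterion 4 admits patients on T-cell immunosuppressants and solid organ transplant recipients, and transplant recipients feature in two of the three randomization strata. What is at stake is the safety of an individual subject in a trial whose primary objective is safety and tolerability.

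**Working it through.** No arithmetic model applies. The check sets the current sections side by side; nothing below comes from the amendment history.

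1. **Which drugs conflict?** The permission sentence in 22.1.2 names five drugs. Their status with voriconazole in 14.4 is:
   - sirolimus: contraindicated (1)
   - tacrolimus, cyclosporine, warfarin: adjust or monitor (3)
   - amiodarone: not listed by name (1)

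   1 + 3 + 1 = 5, so the conflict is confined to 1 drug of 5. Section 14.4 separates sirolimus from the other two immunosuppressants in the sentence; 22.1.2 treats all of them alike.

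2. **Can the permission be used without voriconazole?** No. Section 13.1.1 and footnote t assign voriconazole to both arms. Under Section 11.1.1.1, subjects with possible IPA may already be receiving it during Screening.

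3. **Does a site looking up the rules reach 14.4?** Four places direct it:
   - 12.2, exclusion criterion 2: points to the prohibited list in 22.1
   - 14.1: points to 14.2 and 14.3
   - 14.5: says no restrictions exist beyond 12.2, 13.2 and 14.2
   - 15.28: points to 22.1

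   0 of 4 cite 14.4. Section 14.2 prohibits selected CYP3A4/5 inhibitors, inducers and P-gp substrates, but not CYP3A4 substrates, and sirolimus is not named in 22.1.1. A site following these references arrives at the permission.

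4. **How many subjects could be affected?** SAP Sections 11 and 12 say enrolment stopped at 22 subjects. Neither document gives the number on sirolimus, so the range is 0 to 22.

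**The case against.** The strongest reply is that the contraindication also names the drug, in the main body, directly after 14.3. This is not a specific permission set against general safeguards only. To go wrong, a site must overlook 14.4 as well as the instruction in 22.1.1 to consult and follow the voriconazole label and the rule in 13.1.4 that voriconazole is given per label. The sponsor must then approve the subject (15.3), and medical monitor guidance is available (22.1). A cautious reader would take 22.1.2 as speaking about SCY-078 alone and follow the stricter section.

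This lowers the risk but does not remove the conflict. The words in "permitted for enrollment in the study and these medications may be administered" are about the study, not about SCY-078 alone, and those who approve subjects work from the same two statements. If managed use of sirolimus was intended, 14.4 should say so.

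A reader might be tempted to infer more than the documents support:
- *That subjects received the contraindicated combination or were harmed.* Neither document reports any use.
- *That the safety comparison is biased.* Both arms receive voriconazole under the same co-medication rules, so nothing in the text favours one arm.
- *That 22.1.1 is defective because it omits sirolimus, or should reproduce all of 14.4.* Appendix A describes its contents as examples and sends the reader to the label. The point rests on the permission, not the omission.
- *That the SAP must classify sirolimus use in advance as a deviation.* SAP Section 7.3 already has a category for prohibited or restricted medication with major or minor status; a SAP need not rule on individual drugs.

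**Conclusion.** The protocol is wrong as written on one drug. Sections 22.1.2 and 14.3 cannot both stand with 14.4 in a trial where voriconazole is given to everyone. The matter is an internal inconsistency with a patient-safety consequence, not a flaw in the design or the analysis.

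Its practical size is limited and unknown: between 0 and 22 subjects, possibly none. With enrolment closed, correcting the text protects no further subject in this trial. The conclusion assumes only that 14.4 means what it says. It does not depend on the content of the voriconazole label, which the protocol gives only as a link, or on any assumed harm rate.

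**What to change.** **Text, if it is reused:**
- Remove sirolimus in three places: once in 14.3, once in the permission sentence of 22.1.2 and once in its dose-adjustment sentence.
- Add to both sections an exception for drugs contraindicated with voriconazole in Section 14.4. Deletion alone is not enough in 14.3, because that list is open-ended and 14.4 itself labels sirolimus a CYP3A4 substrate.
- Name sirolimus in 22.1.1 as prohibited during voriconazole treatment, so that exclusion criterion 2 captures it. That criterion works through stated washout periods. The documents give no basis for a length, so the sponsor would have to choose one, bearing in mind the short Screening Period (Days -4 to -1) and that voriconazole may already have been started.

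**This trial:** search the recorded medications for sirolimus. Protocol 14.1 collects all medications from 28 days before Screening through EoT, and SAP 7.7 already summarizes them by preferred term. Report any use, by arm, with the safety results.

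**Cost:** three deletions, two short exceptions, one added entry, and a look through records already held for 22 subjects. Patients who cannot stop sirolimus would be ineligible, which 14.4 already implies.
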